# **SAP Modification History**

The version history of, and modifications to, this statistical analysis plan are described below.

SAP Version	Modification
1.0	Initial
2.0	Update include:
	
 
Use latest HVTN Safety SAP template.
 
Add additional analysis for FSR
 

### 1 LIST OF ABBREVIATIONS AND ACRONYMS

AE Adverse Experience

EAE Expedited Adverse Experience

FSR Final Study Report

RSC Regulatory Support Center SAE Serious Adverse Event SAP Statistical Analysis Plan

STI Sexually Transmitted Infection
DSMB Data Safety Monitoring Board

### 2 OVERVIEW

The following describes the Statistical Analysis Plan (SAP) for the analysis of safety data from HVTN 804/HPTN 095 for Data Safety Monitoring Board (DSMB) reports and the Final Study Report (FSR) for Safety.

### 3 PROTOCOL SUMMARY

**Full title:** Antiretroviral analytical treatment interruption (ATI) to assess immunologic and virologic responses in participants who received VRC01 or placebo and became HIV-infected during HVTN 704/HPTN 085

**Short title:** HVTN 804/HPTN 095 **Sponsor:** NIAID Division of AIDS

Conducted by: HIV Vaccine Trials Network (HVTN) and HIV Prevention Trials Network

(HPTN)

Protocol chairs: [name], MPH; [name]

Sample size: 16 - 46

Study population: HIV-1-infected HVTN 704/HPTN 085 participants who met criteria for

transition to Schedule 2 or Schedule 3 in that trial

**Study design:** An exploratory study of HIV-infected participants undergoing an analytical treatment interruption after receiving VRC01 or placebo infusions in HVTN 704/HPTN 085. The study schema is provided in Appendix I.

**Study duration:** Study duration is potentially indefinite for a participant maintaining extreme and extended viral control during ATI. Study duration for most participants is expected to be 13-18 months. The maximum anticipated duration for any participant is expected to be approximately  $2\frac{1}{2}$  to 3 years.

**Study products:** None. Drugs for anti-retroviral therapy (ART) and for pre-exposure prophylaxis (PrEP) will not be provided by the study or paid for using sponsor funds. Procedures for accessing external funding sources for PrEP and ART provision are detailed in the HVTN 804/HPTN 095 Study Specific Procedures (SSP).

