### 9 SAMPLE SIZE

We calculate the expected trial sized under different scenarios for the percentage of enrolled participants out of the total number of endpoint infected cases from HVTN 704/HPTN 085; scenarios include 25%, 50%, and 75%. Eligible placebo recipients will be capped such that the overall placebo to VRC01 recipient ratio of enrolled participants is at most approximately 1:1. Given that the parent HVTN 704/HPTN 085 study was randomized at a 1:2 placebo to VRC01 ratio, we would only expect to cap the number of eligible placebo recipients if prevention efficacy (PE) exceeds 50%. Given this constraint, along with an assumption of a common prevention efficacy at each dose (PE10 and PE30), the expected trial size will depend on different levels of PE. Under the null hypothesis (PE10 = PE30 = 0%), the total expected number of endpoint infections among placebo recipients is 26 and VRC01 recipients is 55 (Table 4-3 in the parent protocol HVTN 704/HPTN 085); therefore, we assume a trial size of 7, 13 or 20 placebo recipients and 14, 28, or 41 VRC01 recipients depending on the enrollment ratio. Under the alternative hypothesis (PE10 = PE30 = 60%), the total expected number of endpoint infections among placebo recipients is 37 and VRC01 recipients is 30 (Table 4-3 in the parent protocol); therefore, under the different enrollment ratio scenarios, we assume a trial size of 8, 15, or 23 placebo recipients and an equal number of VRC01 recipients so as not to exceed a 1:1 ratio. These six sample size scenarios represent estimated upper and lower bounds for sample size

given the expected number of endpoint infections under the null and alternative hypotheses respectively, as well as various scenarios for the percentage of eligible participants who will ultimately enroll in HVTN 804/HPTN 095.

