### Sample size considerations for time to ART re-initiation criteria (primary objective 1)

Using data from the placebo arm of a therapeutic vaccine study which enrolled early treated patients (80), we modeled the time T (in weeks) to meet re-initiation criteria as a Weibull distribution with survival function  $P(T > t) = \exp[-(\lambda t)p]$ , where  $\lambda = \exp(-2.932) = 0.053$  and p = 2.014. From these parameters, we estimated the median time to meet re-initiation criteria as 15.6 weeks in the AMP placebo recipients. We can express the treatment effect in terms of either the hazard ratio  $\theta$  or the factor  $\beta$  by which treatment increases the median time to meet re-initiation criteria;  $\beta$  and  $\theta$  are related by  $\beta = \theta - 1/p$ .

We model censoring of time to re-initiation criteria using an exponential model and a maximum follow-up time of 72 weeks, where follow-up is censored at a rate of 20% per year due to either study termination or re-initiation of ART before reaching the re-initiation criteria. Simulating 10,000 trials based on these models of time to re-initiation criteria and censoring, we computed power using a log rank test with alpha equal to 0.05. Power for a 40%, 50%, 60%, and 70% reduction in hazard under different enrollment rate and prevention efficacy scenarios are shown in Table 4-1. These hazard reductions correspond to 29%, 41%, 58%, and 82% increases in the median time to meet re-initiation criteria. Therefore, if VRC01 increases the median time to re-initiation criteria 58% and the enrollment rate is 50%, then under the parent study null hypothesis power to detect a difference in time to re-initiation criteria is 72% while under the alternative hypothesis power is 62%.

Table 4-1 Power under different prevention efficacy results, different enrollment rates and different treatment effects, expressed as either reduction in hazard or percent increase in median time to meet re-initiation criteria

		Null hypothesis			Alternative hypothesis		
	25%	50%	75%	25%	50%	75%	
Expected	number of placebos	7	13	20	8	15	23
Expecte	d number of VRC01	14	28	41	8	15	23
Reduction in hazard	% Increase in median time to meet re-initiation criteria				GC	5	75
40%	29%	20%	32%	44%	16%	26%	37%
50%	41%	31%	50%	67%	24%	42%	58%
60% 58%		46%	72%	89%	36%	62%	81%
70%	82%	65%	91%	98%	54%	83%	96%

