### Sample size considerations for safety (primary objective 2)

The goal of the safety evaluation for this study is to identify safety concerns associated with ATI. The ability of the study to detect serious adverse events (SAEs) (see protocol Section 4.2.4.1) can be expressed by the true event rate above which at least 1 SAE would likely be observed and the true event rate below which no events would likely be observed. Under the enrollment rate and PE scenarios described in protocol Section 4.1, Table 4-2 shows the true event rate such that there is a 90% chance of observing at least 1 event (or no events) among three groups; 1) the placebo recipients only, 2) the VRC01 recipients only, or 3) all enrolled participants.

Table 4-2 True event rates above which at least 1 SAE (or below which no events) would likely be observed in a group of size n participants. Event rates are computed separately for various values of n given by the range and midpoint for the estimated number of participants among 3 groups; 1) the placebo recipients only, 2) the VRC01 recipients only, or 3) all enrolled participant based on the enrollment scenarios described in Section 4.1.

	Placebo recipients			VRC01 recipients			All enrolled		
71	7	15	23	8	25	49	16	38	61
At least 1 event	28.0%	14.2%	9.5%	25.0%	8.8%	4.6%	13.4%	5.9%	3.7%
No events	1.5%	0.7%	0.5%	1.3%	0.4%	0.2%	0.7%	0.3%	0.2%

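### Section 3 gives a sample size of 16 to 46, but section 9 and both tables run to 61, and the largest VRC01 group in Table 4-2 (49) matches no scenario

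*SAP*

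**What the plan says.** Section 3 (Protocol Summary) states "Sample size: 16 - 46" without qualification.

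Section 9 derives the size from expected infections in the parent trial and enrolment of 25%, 50% or 75%. Under the null, "the total expected number of endpoint infections among placebo recipients is 26 and VRC01 recipients is 55", so "we assume a trial size of 7, 13 or 20 placebo recipients and 14, 28, or 41 VRC01 recipients depending on the enrollment ratio". For the alternative it expects 37 placebo and 30 VRC01 infections and, with placebo capped at about 1:1, takes 8, 15 or 23 per group. It then says: "These six sample size scenarios represent estimated upper and lower bounds for sample size", linking these bounds to the null and alternative hypotheses respectively.

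Table 4-1 gives power for these six pairs of group sizes, including 20+41.

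On safety the SAP says: "Under the enrollment rate and PE scenarios described in protocol Section 4.1, Table 4-2 shows the true event rate". The group sizes are described as the range and midpoint of the scenario numbers. Those printed are placebo 7/15/23, VRC01 8/25/49 and all enrolled 16/38/61.

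**The concern.** Two figures do not fit the derivation they are meant to summarise.

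- **The upper limit of 46.** This is the largest alternative-hypothesis scenario (23+23). Section 9 takes its upper bounds from the null scenarios, whose maximum is 61. A reader of section 3 would think the trial stops at 46, while the most favourable power and SAE figures rest on 61.
- **The VRC01 maximum of 49.** Section 9 and Table 4-1 both stop at 41. A larger group lowers the SAE rate that the study appears able to detect, so the error is in the reassuring direction. This matters somewhat because the SAP governs the safety reports to the DSMB and the safety Final Study Report.

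**Working it through.** **1. Scenario sizes.** Inputs from section 9: 26 placebo and 55 VRC01 infections under the null; 30 VRC01 infections under the alternative, matched 1:1.

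| Enrolment | Null: placebo + VRC01 | Total | Alternative: per group | Total |
|---|---|---|---|---|
| 25% | 6.5 → 7; 13.75 → 14 | 21 | 7.5 → 8 | 16 |
| 50% | 13; 27.5 → 28 | 41 | 15 | 30 |
| 75% | 19.5 → 20; 41.25 → 41 | 61 | 22.5 → 23 | 46 |

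Section 9's group sizes are reproduced. The range over all six scenarios is 16 to 61; 16 to 46 is the alternative alone. Leaving placebo uncapped under the alternative (37 × 75% = 27.75, with 22.5 VRC01, about 50 in total) does not explain 46 or 49 either.

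**2. Table 4-2.** The rate giving a 90% chance of at least one event is 1 − 0.1^(1/n). The rate giving a 90% chance of none is 1 − 0.9^(1/n). These reproduce every printed cell at its printed n. The relevant values are:

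| n | At least 1 event | No events | Printed |
|---|---|---|---|
| 8 | 25.01% | 1.308% | 25.0% / 1.3% |
| 25 | 8.80% | 0.421% | 8.8% / 0.4% |
| 41 | 5.46% | 0.257% | not shown |
| 49 | 4.59% | 0.215% | 4.6% / 0.2% |
| 61 | 3.70% | 0.173% | 3.7% / 0.2% |

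The printed 4.6% fits n=49 only (48 gives 4.7%, 50 gives 4.5%). So 49 is not a misread digit, and correcting the header alone would leave wrong rates below it.

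**3. Whether 49 can arise.** 49/55 = 89.1% enrolment, above the highest scenario of 75%; 41/55 = 74.5%. The printed midpoint of 25 is near (8+41)/2 = 24.5 and not near (8+49)/2 = 28.5.

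**4. Consequence for SAE detection.** At a true rate of 4.6%, 41 recipients give 1 − 0.954^41 = 85.5% chance of at least one SAE, not 90%.

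**5. Table 4-1.** Re-simulation used the SAP's model: Weibull with λ = exp(−2.932) and p = 2.014, exponential censoring at 20% per year, a 72-week maximum, and a log-rank test at two-sided 0.05. The first, second and last rows used 20,000 trials per cell; the 20+49 row used 10,000.

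| Placebo + VRC01 | Power at 40/50/60/70% hazard reduction | SAP |
|---|---|---|
| 20+41 | 43.6/67.2/88.4/98.4% | 44/67/89/98% |
| 23+23 | 36.2/57.5/80.7/95.4% | 37/58/81/96% |
| 20+49 | 45.8/69.5/90.8/99.1% | – |
| 15+31 (assumed) | 35.2/55.1/77.8/94.4% | – |

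Table 4-1 is therefore right for the sizes it shows, and its top null scenario used 41, not 49. The 15+31 row splits 46 in the ratio 20:41 (46 × 20/61 = 15.1; 46 × 41/61 = 30.9). That split is an assumption; the SAP gives none.

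**The case against.** The strongest reply is that this is editorial. The study is exploratory with no fixed size, no formal between-arm safety test is planned, and no rule or analysis in the SAP uses the Table 4-2 rates. Every printed rate is correct for the n shown, and Table 4-1 prints its group sizes, so no stated power is wrong for its column. This stands, and it keeps the point modest. It does not remove the contradiction between sections 3 and 9, or justify an n that no scenario produces.

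It can also be said that section 3 summarises a protocol not shown here, so which figure governs cannot be settled from the SAP. That is correct, and for that reason the remedy has two branches. The SAP states a cap on the placebo ratio but none on the total, so a true maximum of 46 is only a possibility and the 15+31 split only an illustration.

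Two supporting arguments carry limited weight. Subtracting 49 from 61 leaves 12 placebo recipients, a number in no scenario. But the table computes its groups separately and the column maxima need not add up (23+41=64 is not 61 either). The midpoint argument is suggestive only: 24.5 is printed as 25, while (16+61)/2 = 38.5 is printed as 38. The enrolment fraction of 89% is sufficient without them.

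**Conclusion.** Both inconsistencies hold. On section 9's own inputs the range is 16 to 61, so section 3's upper limit is 15 below it. The last VRC01 column of Table 4-2 should read 5.5% / 0.3% at n=41 instead of 4.6% / 0.2%. The first changes by 0.9 percentage points (5.46 against 4.59); the second is mostly rounding (0.257 against 0.215). This assumes that section 9 is the governing statement.

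If 46 is instead a real maximum, the 20+41 column is not attainable. At a 60% hazard reduction, power in a trial of 46 would be about 78% (15+31, assumed) to 81% (23+23), against the 89% shown for 20+41.

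The correction should be made because a stated sample size and a safety column are wrong as they stand. It affects no endpoint or analysis method.

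**What to change.** Check section 3, section 9 and Table 4-2 against the protocol, then take one of two routes.

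- **Section 9 stands.** State 16-61 in section 3, and change the last VRC01 column of Table 4-2 from 49 to 41, with 5.5% and 0.3%. Table 4-1 needs no change. Cost: one line and one column.
- **46 is a real maximum.** Say so in section 9 and state how a capped 46 divides between VRC01 and placebo. Recompute the 20+41 column of Table 4-1, and the midpoint and maximum columns for VRC01 and all enrolled in Table 4-2. With all-enrolled sizes of 31 (the midpoint of 16 and 46) and 46, the rates are 7.2% / 0.3% and 4.9% / 0.2%. For illustration only, a 15+31 split would give about 35/55/78/94% in Table 4-1 and 7.2% / 0.3% for 31 VRC01 recipients. Cost: a short statement in section 9 and the affected columns.

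Neither route changes trial conduct or the analysis methods.

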### 4 HYPOTHESIS

### 4.1 Primary hypothesis

- VRC01 recipients who became HIV-infected during HVTN 704/HPTN 085 within 8 weeks of their last study product administration will suppress plasma viremia and maintain CD4+ T-cell counts longer during ATI than placebo recipients who became HIV-infected during HVTN 704/HPTN 085.
- ATI will be safe and well-tolerated in individuals who became HIV-infected in HVTN 704/HPTN 085

### 4.2 Secondary hypothesis

- VRC01 recipients who became HIV-infected during HVTN 704/HPTN 085 within 8 weeks of their last study product administration will have enhanced cellular and humoral responses compared to placebo recipients who became HIV-infected during HVTN 704/HPTN 085.
- VRC01 recipients who became HIV-infected during HVTN 704/HPTN 085 within 8 weeks of their last study product administration will have more limited viral reservoirs, before and after ATI, than placebo recipients who became HIV-infected during HVTN 704/HPTN 085.

### 5 SAFETY/VIROLOGIC(?) OBJECTIVES AND ENDPOINTS

Primary objective 1

• To evaluate the effect of VRC01 received in the immediate pre-HIV acquisition period and/or during early infection on the time to meeting ART re-initiation criteria in participants undergoing ATI

Primary endpoint 1

- Time to meeting criteria for ART re-initiation
- Frequency of sustained post-treatment HIV control, defined as  $\geq$  24 weeks off ART without meeting ART re-initiation criteria

Primary objective 2

• To evaluate the safety of ATI among HVTN 804/HPTN 095 participants

Primary endpoint 2

• Laboratory measures of safety, adverse events (AEs), SAEs (serious AEs), and rates of discontinuation

Secondary objective 2

• To evaluate the effect of VRC01 received in the immediate pre-HIV acquisition period and/or during early infection on viral load in participants undergoing ATI

Secondary endpoint 2

• Cumulative incidence of participants with viral load  $\geq$  200 at weeks 8, 16, and 24

Secondary objective 3

• To evaluate the effect of VRC01 received in the immediate pre-HIV acquisition period and/or during early infection on HIV reservoir size before and after ATI, and whether HIV reservoir measurements are associated with time to meeting criteria for ART reinitiation in participants undergoing ATI

Secondary endpoint 3

• Frequency of CD4+ T cells carrying intact and/or total pro-viral HIV DNA, replication competent virus, and/or cell-associated HIV RNA

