### 10.3.1 Time to ART re-initiation

The primary outcome is the time from the start of treatment interruption until the participant meets criteria to re-initiate ART.

A Cox proportional hazards model with the indicator of assignment to a mAb group versus the control group will be used to estimate the cumulative incidence in each of the infected VRC01 and infected placebo groups, as well as the hazard ratio, all with 95% confidence intervals and associated 2-sided p-values, where the model controls for baseline covariates thought to potentially predict both HIV-1 infection and the instantaneous hazard of meeting the ART reinitiation criteria. This is needed for controlling for potential postrandomization selection bias given that analyzed treatment groups are selected postrandomization. Plots of the estimated cumulative incidence will be shown by treatment group.

As a supportive analysis of this hypothesis, targeted minimum loss-based estimation (TMLE) may be used to estimate cumulative incidences of the primary efficacy endpoint over time for the pooled mAb arm and the control arm. Iterative mean-based TMLE is used for this analysis as described by Benkeser et al (2). The Super Learner (3) is used to generate initial estimates of the conditional censoring distribution and the iterated conditional means. This analysis will use TMLE as implemented in the R package survtmle available on CRAN (4).

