### 10.3.2 Frequency of sustained post-treatment HIV control

The same covariate adjusted model used to estimate cumulative incidence of meeting the reinitiation criteria for ART over time, described in the previous section, will be used to compare the rates of failure to maintain HIV control at 24 weeks between the two treatment groups.

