### 10.4.3 Reasons for discontinuation of ATI and early study termination

The number and percentage of participants who discontinue ATI and who terminate the study early will be tabulated by reason and treatment arm.

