### 11.2 List of Figures

These graphs are included in the DSMB reports and FSR for Safety:

- Longitudinal Summaries of HIV-1 RNA Viral Load and CD4+ T-Cell Count (participant level) – all participants
- Longitudinal Summaries of HIV-1 RNA Viral Load and CD4+ T-Cell Count, restricted to participants who entered schedule 2 and to schedule 1 and 2 data points
- Cumulative Incidence of Meeting ART Re-Initiation Criteria
- Survival Plot of Time to Viral Load ≥ 200 (copies/ml)

Additional graphs included in FSR for Safety:

• Boxplots for local laboratory value (ALT, Direct Bilirubin, eGFR, Hemoglobin, Platelets, Absolute Neutrophil Count) at schedule 1 (visit 4, 8, 12, 14, 16, 18, 20, 21, 22, 23, 25, 27), schedule 2 (visit 40, 44, 48, 50, 52, 54, 56, 58, 60, 62, 64, 66), and schedule 3 (82, 84, 86, 89, 91)

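### Sustained control is worded as 24 weeks off ART, but SAP 10.3.2 takes it from a model whose only event is meeting re-initiation criteria, so an ART restart before criteria never counts as failure

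*SAP*

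**What the plan says.** - **Endpoint (SAP section 5, primary endpoint 1).** Besides time to criteria, the endpoint includes the frequency of sustained post-treatment control, meaning at least "24 weeks off ART without meeting ART re-initiation criteria". Read literally, this sets two conditions: still off ART at 24 weeks, and criteria not met.
- **Model (SAP 10.3.1).** The outcome is the "time from the start of treatment interruption until the participant meets criteria to re-initiate ART". That is the only event. The supportive TMLE uses the Super Learner to "generate initial estimates of the conditional censoring distribution and the iterated conditional means", without saying what counts as censoring.
- **Analysis of sustained control (SAP 10.3.2).** "The same covariate adjusted model used to estimate cumulative incidence of meeting the reinitiation criteria for ART over time" is reused to "compare the rates of failure to maintain HIV control at 24 weeks between the two treatment groups".
- **Planning (SAP section 9, time to re-initiation criteria).** The simulation censors follow-up at 20% per year, "due to either study termination or re-initiation of ART before reaching the re-initiation criteria". The split between these two causes is not given.
- **Reporting.** Section 10.4.3 says that "participants who discontinue ATI and who terminate the study early will be tabulated by reason and treatment arm". Section 11.2 lists a figure titled "Cumulative Incidence of Meeting ART Re-Initiation Criteria".

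**The concern.** The endpoint has two conditions and the model enforces one. Someone who goes back on ART at week 12 without meeting criteria fails the definition, but nothing in 10.3.1 or 10.3.2 makes that person a failure. The SAP itself foresees the case, since its power simulation names it as a cause of censoring.

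This is part of a primary endpoint. If restart is censored in the analysis as it was in planning, the model estimates the probability of not meeting criteria had nobody restarted. That needs restart to be independent of time to criteria given the covariates, an assumption the SAP does not state. With planned groups of 7 to 41, the handling of one or two people can change the reported frequency, so it is better fixed before the data are seen.

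**Working it through.** **Inputs, all from SAP section 9.** Weibull time to criteria with λ = exp(−2.932) = 0.0533 per week and p = 2.014; censoring 20% per year; maximum follow-up 72 weeks; group sizes 7 to 23 (placebo) and 8 to 41 (VRC01). A hazard ratio of 0.4 (60% reduction) serves as the worked case. Two assumptions are added: restart is independent of time to criteria, and restart makes up between none and all of the 20% per year.

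**Reproducing the plan.** The placebo median is (ln 2)^(1/p)/λ = 15.64 weeks (stated 15.6). A simulation of 10,000 trials per cell with a two-sided log-rank test gives power of 72.5% and 61.3% at a 60% reduction and 50% enrollment (stated 72% and 62%). All 24 cells of Table 4-1 agree within 2 points, so the inputs are read as the SAP used them.

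**Control from the criteria-only model at week 24.** S(24) = exp[−HR × (λ × 24)^p], with (0.0533 × 24)^2.014 = 1.641.
- Placebo: exp(−1.641) = 19.4%.
- VRC01: exp(−0.4 × 1.641) = 51.9%.

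**Control as worded.** Multiply by k, the probability of no restart by week 24. The hazard is h = −ln(0.8)/52 = 0.00429 per week. If all censoring is restart, k = exp(−24h) = 0.902; if half is, k = exp(−12h) = 0.950.

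| Restart share of censoring | Placebo | VRC01 | Excess of model over definition (points) |
|---|---|---|---|
| none | 19.4% | 51.9% | 0 / 0 |
| half | 18.4% | 49.3% | 1.0 / 2.6 |
| all | 17.5% | 46.8% | 1.9 / 5.1 |

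In participants, n × S(24) × (1 − k) with all censoring as restart is 0.1 to 0.4 in placebo and 0.4 to 2.1 in VRC01.

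**Between-arm difference.** The model gives 51.9 − 19.4 = 32.5 points. As worded:

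| Who restarts | At 20% per year | At half that rate |
|---|---|---|
| both arms | 29.3 | 30.9 |
| VRC01 only | 27.4 | 29.9 |
| placebo only | 34.4 | 33.5 |

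The sign of the shift therefore depends on which arm restarts more.

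**Against sampling error.** With sqrt[S(1 − S)/n], the simple binomial standard error is 7.8 points for VRC01 at n = 41, and 11.8 points for the difference at 20 and 41. Every shift above is smaller.

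**Direction.** For the underlying probabilities, and for an unadjusted Kaplan-Meier curve, adding restarts as events can only lower control. A fitted Cox model with one shared baseline is different, because the added events move the hazard ratio and the baseline together. Cox fits were simulated under the planning model (HR 0.4, all censoring taken as restart, no covariates) and compared with and without restart as an event, in trials with at least one early restart. The mean change was about −2 points in placebo and −5 in VRC01. Counting restarts nevertheless raised fitted placebo control in about one trial in five at 20/41, 26% at 13/28 and 33% at 7/14.

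**The case against.** The best defence is that off ART names only the clock. The related objective is time to meeting criteria, the endpoint is called HIV control, and the primary hypothesis concerns suppression of viremia. A person who restarts for a non-virologic reason has not lost virologic control. On that reading censoring is appropriate, and sections 5 and 10.3.2 agree. This reading is available and stands as an alternative, but the SAP does not adopt it, and the literal wording makes time off ART part of the definition.

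Other points stand in full. Censoring of restart is stated only for the power simulation. A reader might infer from the TMLE text that restart is also censored in the analysis; that text does not show it, since any right-censored analysis with dropout needs a censoring distribution. The protocol, which is not shown here, may say how restarts are handled, and how many would fall outside the criteria cannot be judged. The upper end of the range requires all censoring to be restart, whereas the SAP names study termination as well. The study is described as exploratory, and 10.4.3 would make early restarts visible, though only in a table.

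A reader might also infer that every reported arm estimate will overstate control, or that the comparison is tilted towards VRC01. Neither follows: the direction holds on average for the level, and the difference can move either way.

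**Conclusion.** The point holds in a limited form. The method in 10.3.2 does not deliver the endpoint as section 5 literally words it, because a foreseen route to failing the definition is not a failure in the model. Under the planning model at HR 0.4 the average excess is 0 to 1.9 points in placebo and 0 to 5.1 in VRC01, and it is zero if nobody restarts early before week 24. The size rests on the assumed restart share and on independent restart; the average direction does not rest on independence.

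It would be going too far to conclude that primary objective 1 or its power is compromised. Time to criteria is a separate outcome with its own event, and Table 4-1 reproduces as stated. Severity is minor: the gap is small and may be near zero, but it concerns part of a primary endpoint and is cheap to close.

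**What to change.** In 10.3.2, fit the same covariate-adjusted model to failure defined as meeting criteria or restarting ART before week 24, whichever comes first, and censor only study termination or loss to follow-up. Report the criteria-only version alongside as a sensitivity analysis, with restart censored and the independence assumption given the covariates written out. In 10.3.1, leave time to criteria as it is and add that restart before criteria is censored at the restart date.

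If the sponsor instead means control had ART not been restarted, reword the endpoint in section 5 to say so, state the same assumption, and make the composite the sensitivity analysis.

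The cost is a few sentences and one derived variable, assuming that restart dates before criteria are recorded. With the composite, reported control would be slightly lower on average, non-virologic restarts count as failures, and the week-24 result no longer reads directly off the cumulative incidence figure in 11.2.
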